## **5.4 Adherence Assessment**

Adherence to group yoga and physical conditioning classes will be documented by the study class instructors using standardized attendance logs. Attendance logs will be returned to clinical coordinators on at least a weekly basis throughout the yoga therapy and physical conditioning programs. Clinical coordinators will immediately contact any participant who misses a scheduled class to ask about reasons for missing the class, reinforce the importance of class attendance, and troubleshoot any barriers to attendance.

Adherence to home practice of yoga or stretching/strengthening exercises will be tracked using home practice logs. Participants will be instructed to record the date, time, and duration of each home practice session in their logs, as well as the specific yoga poses or stretching/strengthening exercises practiced during each session. Home practice logs will be collected by class instructors and returned to the clinical coordinators on a weekly basis during the 12-week treatment program. Clinical coordinators will contact any participant whose log indicates that she is not practicing yoga or stretching exercises at least one hour a week at home. Additionally, home practice logs will be returned by mail 12 weeks after the end of the intervention program to assess home practice during the post-treatment follow-up period.

Every effort will be made to encourage participants to complete all intervention classes and practice sessions. Prior to randomization, study coordinators will stress the importance of adherence to group classes and home practice, and only those women who indicate that they are available on scheduled class dates and willing to practice yoga or stretching exercises at home as recommended will be eligible for randomization. The importance of adherence will again be stressed at the orientation session for each yoga or physical conditioning series, as well as during follow-up telephone calls 2 weeks and follow-up visits at 8 weeks. Additionally, attendance sheets from yoga and stretching classes will be carefully monitored, and home practice logs will be reviewed weekly, so that study staff can immediately call any women who miss classes or fail to document home practice in order to reinforce the importance of attendance/practice and troubleshoot barriers to adherence.

## 6. STUDY PROCEDURES

### 6.1 Study Measures

#### 6.1.1 Urinary Incontinence

The primary efficacy outcome, frequency of any urinary incontinence, will be assessed using a 3-day voiding diary that has been shown to be a valid and reliable method for documenting change in incontinence symptoms and is widely used in clinical trials of incontinence treatments. At screening/baseline, 8 weeks, 12 weeks, and 12 weeks after the end of the yoga and physical conditioning programs (24 weeks), each participant will receive written instructions and a blank diary to take home, and will use the diary to record all voiding and incontinence episodes over a 3-day period and classify incontinence episodes by clinical type (urgency, stress, other). Upon return of the diary, an analyst will abstract data to determine the number of total as well as urgency and stress incontinence episodes per day. For diaries that are completed after randomization, data will be abstracted by an analyst who is blinded to treatment assignment.

#### 6.1.2 Condition-Specific Quality of Life

To address incontinence-related quality of life, participants will complete the following validated questionnaire measures at baseline, 8 weeks, and 12 weeks, as well as 12 after the end of the yoga and physical conditioning programs (24 weeks):

- A. Incontinence Impact Questionnaire (IIQ)-- a validated, 28-item measure of the impact of incontinence on 4 domains of functioning and quality of life (physical activity, emotional health, relationships, and travel). Scores range from 0 to 100; higher scores indicate worse impact.
- B. Urogenital Distress Inventory-6 (UDI-6)-- a validated, 6-item measure that assesses subjective distress from frequent urination, urgency incontinence, stress incontinence, small-volume leakage, difficulty emptying the bladder, and genital pain. Scores are scaled from 0 to 100.
- C. Patient Perception of Bladder Condition (PPBC)-- a validated single-item measure assessing the degree to which respondents consider their condition to be a problem on a 6-point scale.

### **6.1.3 Anxiety and Perceived Stress**

To evaluate anxiety and perceived stress symptoms that may be associated with incontinence, participants will complete the following validated questionnaire measures at screening/baseline, 8 weeks, and 12 weeks, as well as 12 weeks after the end of the yoga and physical conditioning programs (24 weeks):

- A. Spielberger State Trait Anxiety Inventory (STAI): Somatic anxiety (i.e., the affective component of anxiety believed to be related to autonomic physiological arousal response) will be measured using the trait component of the STAI, a 20-item self-administered measure validated in clinical populations, including patients with bladder symptoms, with scores ranging from 20 to 80.
- B. Hospital Anxiety and Depression Scale (HADS): Cognitive anxiety (i.e., the mental component of anxiety associated with fear of failure) will be measured by the HADS, a validated self-administered questionnaire that includes a 7-item Anxiety Subscale shown to be sensitive to change in incontinence trials. Scores range from 0 to 21, with higher scores indicating greater anxiety.
- C. Perceived Stress Scale (PSS): Perceived stress will be assessed by the PSS, a 10-item measure of thoughts and feelings related to perceived stress in the past month, validated in a probability sample of the United States. Scores range from 0 to 40; higher scores indicated greater stress.
- D. Center for Epidemiologic Studies Depression Scale (CES-D): Depressive symptoms will be assessed by the CES-D, a 20-item measure that has been widely used in clinical trials, including bladder interventions, and is sensitive to change. Total scores range from 0 to 60.

### **6.1.4 Yoga/Physical Conditioning Self-efficacy and Competency**

- A. Yoga Posture Self-Efficacy: At 8 weeks and 12 weeks, as well 12 weeks after the end of the yoga therapy program (24 weeks), women in the yoga group will complete a structured questionnaire (modeled after an existing self-efficacy measure and pre-tested in the investigators' previous pilot study) to indicate how confident they are that they can perform each of the postures featured in the program (from 'not at all' to 'extremely confident'). Total scores will range from 0 to 56, with higher scores indicating greater confidence. A corresponding questionnaire will be administered to the physical conditioning group participants.
- B. Independent Yoga Competency Assessment: To provide a more objective assessment of women's success in learning yoga, a yoga expert consultant will attend one class at the end of each series and observe women as they practice yoga. The consultant will rate each woman's success in performing each yoga posture on a 5-point scale, ranging from "not at all" to "extremely" successful. Total scores will range from 0 to 56. In the physical conditioning control group, [name], DPT, will provide similar assessments.
- C. Yoga Practice Adherence Self-Efficacy: At 8 weeks and 12 weeks, as well 12 weeks after the end of treatment (24 weeks), women will complete a measure of confidence in adhering to yoga or stretching practice, modeled after existing physical activity adherence self-efficacy scales and tested

in the pilot study. Women will indicate on a 5-point scale how confident they are that they can practice yoga or stretching when they: 1) are tired, 2) are in a bad mood, 3) have limited time, 4) are away from home, and 5) are not regularly attending yoga classes. Scores will range from 0 to 20.

D. Credibility and Expectations of Treatment: To assess whether women perceive the yoga and physical conditioning interventions as equally credible and have similar expectations for improvement in incontinence, we will administer a modified version of an expectancy/credibility measure used in other women's health studies at baseline.

#### 6.1.5 Additional Screening and Covariate Measures

The following data will be collected to assess eligibility, assess whether treatment groups are comparable at baseline, and guide statistical adjustments in the event groups are not balanced:

- A. Demographic history including date of birth, gender/sex, race/ethnicity, education history, employment history, marital status (screening/baseline)
- B. Urologic/urogynecologic history including age of onset of incontinence, past and current treatment of incontinence, history of pelvic surgery, history of pregnancy and delivery, menstrual/menopausal status (screening/baseline)
- C. General medical history including general health assessed by the CDC Healthy Days module, selected medical conditions associated with incontinence such as diabetes, and current medication use (screening/baseline and 12 weeks)
- D. Health-related habits such as tobacco/alcohol use, prior yoga experience, prior group-based physical activity instruction, physical activity level by the International Physical Activity Questionnaire (screening/baseline)
- E. Sleep quality assessed using the Pittsburgh Sleep Quality Index (PSQI), a validated questionnaire evaluating sleep quality, latency, efficiency, and problems (screening/baseline, 8 weeks, 12 weeks, 24 weeks)
- F. Physical exam measures including measured height, weight, heart rate, and blood pressure (screening/baseline, 8 weeks, and 12 weeks)
- G. Physical function including self-reported function using the PROMIS Adult Physical Function Profile short-form. Participants will also undergo direct physical mobility evaluation using the Short Physical Performance Battery (screening/baseline, 8 weeks, and 12 weeks).

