### **9.8 Data Analyses**

To address aim 1 (feasibility), descriptive statistical techniques will be used to describe rates of recruitment, randomization, retention, and adherence for each recruitment wave. If drop-out is substantial, we will conduct exploratory pooled logistic regression analyses to try to identify participant characteristics associated with drop-out. Similarly, if adherence is less than expected, we will use linear, logistic, and/or proportional odds models, depending on the distribution of the outcome, to explore associations of participant characteristics with levels of adherence both to classes and home practice.

To address aim 2 (preliminary efficacy for change in incontinence frequency), we will use linear mixed models with unstructured residual covariance matrix to conduct a preliminary analysis of the 8, 12, and 24 week changes from baseline in incontinence frequency, adjusting for the baseline values, and treating week as categorical. This will provide estimates of the residual standard deviation, intra-class correlation, and fitted between-group differences at each follow-up time point. To assess trends and persistence, we will compare estimated between-group differences across weeks. All estimates will be presented with 95% confidence intervals.

The methods specified for aim 2 will also be used for aim 3 (preliminary efficacy for secondary symptom and quality-of-life outcomes). Outcomes will be normalized as necessary before analysis, and checked for equal variance across group and visit. In previous studies, changes in incontinence frequency and in other symptom and quality-of-life scores have been approximately normally distributed.

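### Section 6.1.5 lets observed baseline imbalance guide covariate adjustment, with no criterion for imbalance and no stated place beside the section 9.8 model

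*Combined protocol and SAP*

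**What the plan says.** Section 6.1.5 introduces its list of screening and covariate measures with their purposes: eligibility, and then to "assess whether treatment groups are comparable at baseline, and guide statistical adjustments in the event groups are not balanced". Items A to G follow. They cover demographics, urogynecologic and general medical history, health habits, sleep quality, physical examination, and physical function. The section gives no test, threshold or ranking of variables, and does not say what an adjusted analysis would be used for.

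Section 9.8 sets the efficacy analysis for Aims 2 and 3. It is a linear mixed model of change from baseline with unstructured residual covariance, "adjusting for the baseline values, and treating week as categorical". The model yields the residual SD, the intra-class correlation and the between-group differences, all with 95% confidence intervals. No 6.1.5 variable is named, and no step depends on baseline balance.

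Sections 1 (Aim 2) and 9.2 say that the SD, the intra-class correlation and the between-group difference will guide sample size projections for a full-scale trial. Section 9.2 plans up to 90 women, about 45 per arm, and reports no formal sample size calculation.

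**The concern.** Allocation is randomized and concealed (sections 6.2.4 and 9.3), so any baseline difference between the arms arises by chance. The size of a chance difference says nothing about whether the variable predicts incontinence frequency, and prediction is what makes a covariate worth having. Letting imbalance guide the choice makes the model depend on the data, and tends to bring in covariates that are correlated with treatment in the sample at hand.

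The estimates are this pilot's product. A between-group difference and residual SD from a covariate set picked by chance do not correspond to a model that the next trial can specify in advance.

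Timing adds to this. Under section 6.2.4 the investigators and the outcome abstractors stay blinded until the dataset is locked. For them, balance by group would normally become visible only when outcomes by group are available too. An undefined rule applied at that point leaves room to choose between two estimates of the same quantity.

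**Working it through.** The plan states no figure on this point, so there is none to reproduce. The imbalance threshold, the correlations among covariates and their prognostic strength below are assumptions, because the documents give none.

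**1. Number of variables in 6.1.5**
- A, "Demographic history including date of birth, gender/sex, race/ethnicity, education history, employment history, marital status": 6
- B, "age of onset of incontinence, past and current treatment of incontinence, history of pelvic surgery, history of pregnancy and delivery, menstrual/menopausal status": 5
- C, general health plus "selected medical conditions associated with incontinence such as diabetes, and current medication use": 3
- D, "Health-related habits such as tobacco/alcohol use, prior yoga experience, prior group-based physical activity instruction, physical activity level": 4
- E, sleep quality: 1
- F, "Physical exam measures including measured height, weight, heart rate, and blood pressure": 4
- G, self-reported function and the mobility battery: 2

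The total is 6+5+3+4+1+4+2 = 25. Sex is constant in an all-women trial, which leaves 24; splitting compound items gives about 28.

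**2. Chance that at least one variable is flagged.** For k independent variables each flagged with probability a, the chance is 1 − (1 − a)^k. For a standardized mean difference (SMD) with 45 per arm, the standard error is √(2/45) = 0.211. Then |SMD|>0.5 has a = 0.018 and |SMD|>0.25 has a = 0.236.

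| Assumed rule | k = 24 | k = 25 |
|---|---|---|
| p<0.01 | 21.4% | 22.2% |
| p<0.05 | 70.8% | 72.3% |
| p<0.10 | 92.0% | 92.8% |
| SMD above 0.5 | 34.9% | 36.0% |
| SMD above 0.25 | 99.8% | 99.9% |

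The number flagged by chance at p<0.05 is 24 × 0.05 = 1.2 on average. In simulation, pairwise correlation of 0.1 or 0.3 lowers the p<0.05 figure to about 69% or 60%. If only 20 variables carry usable variation, it is 1 − 0.95^20 = 64.2%.

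**3. Interval width after adding one flagged covariate.** The multiplier is √[(1 − R²)/(1 − r²) × (n − 3)/(n − 4)]. Here r² = t²/(t² + n − 2) is the squared correlation between covariate and arm, and R² is the covariate's partial R² for the outcome. Take a just-flagged covariate, t = 1.987.
- n = 90: r² = 3.948/91.948 = 0.043. With R² = 0 the multiplier is √(1/0.957 × 87/86) = 1.028. With R² = 0.05, 0.10 and 0.20 it is 1.002, 0.975 and 0.920. Break-even is at R² of about 5–6%.
- n = 72 (90 less 20% drop-out, the limit in section 9.7.1): r² = 0.053, and the multiplier at R² = 0 is 1.035.

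**4. Simulation of the whole rule.** Settings: 24 covariates, p<0.05 screen, n = 90 or 72, correlation 0 to 0.3, 1,500 trials each, single-time-point ANCOVA. When the screen is triggered:
- the mean width ratio is 1.05–1.07 if no covariate is prognostic;
- it is 0.955–1.065 if the covariates jointly explain 20–40% of variance;
- coverage is about 94–97% throughout.

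**5. Movement of the estimate, and the alternative.** In a further simulation with 45 per arm and 24 covariates under the same screen, the estimate moved by more than half a standard error in 14–31% of triggered trials. Type I error stayed at 4–5%. With three prognostic covariates jointly explaining 15% of variance, naming them in advance gave a mean standard error of 0.198, against 0.218 under the imbalance rule.

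**6. Effect on the planning SD.** A covariate with partial R² of 0.20 multiplies the residual SD by √0.80 = 0.894. Sample size is proportional to the SD squared, so the projection would fall by 20%. A covariate with no prognostic value leaves the residual SD nearly unchanged.

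**The case against.** The strongest reply is that 6.1.5 is a data-collection section. It says that the measures will guide adjustment, not that every unbalanced variable enters the model. The efficacy analysis is set in 9.8, and the trial is a pilot not powered to test hypotheses. Much of this stands, and it rules out several stronger readings that a reader might infer.

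- *The rule will usually be triggered.* That depends on a threshold the plan does not give; the table runs from about 21% to over 99%. Exclusion criteria also reduce variation in items such as current treatment, recent pelvic surgery and medication use, and several items are plausibly correlated.
- *Adjustment always widens the intervals.* It does not. Sufficiently prognostic covariates narrow them, and the list includes conditions chosen for their association with incontinence.
- *The rule conflicts with 9.8.* Section 9.8 is silent on an imbalance step; 6.1.5 adds one without contradicting it.
- *6.1.5 proposes adjusting for measures taken after randomization.* Its purpose sentence concerns comparability at baseline, and the week 8, 12 and 24 entries are visit schedules.
- *Type I error is inflated.* Under the rule itself it is not. A figure of about 6% arises only if someone reports the smaller of two p-values, which nobody has planned.

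What the reply does not remove is the gap. The plan announces adjustment guided by imbalance, defines neither the trigger nor the status of the result, and names no prognostic covariate in its place.

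**Conclusion.** The concern holds as a weakness in how the covariates are chosen. The plan ties adjustment to chance imbalance across about 25 variables and leaves the criterion and the role of the adjusted result open. Covariates fixed in advance on prognostic or design grounds are a better method at almost no cost.

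The size is moderate. At an assumed p<0.05 screen, about 60–72% of trials would have a flagged variable. The cost is roughly 3–7% in interval width when the flagged variables are weakly or not prognostic, with coverage near nominal. The larger consequence is that the difference and residual SD carried into the next trial's sample size could depend on which variables happened to differ. The simulations analyse a single time point, not the three-visit mixed model of 9.8, so their figures are indicative. The choice of method does not depend on them.

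**What to change.** In 6.1.5, delete the part of the quoted purpose sentence after its comma, leaving eligibility and baseline comparability as the stated purposes.

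In 9.8, state that:
- the baseline-adjusted mixed model gives the main estimate for Aims 2 and 3;
- any further covariates in it are baseline variables named now on prognostic or design grounds, and used whatever the balance;
- any adjustment guided by observed imbalance is a labelled sensitivity analysis.

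Incontinence type is a natural candidate on design grounds: it is the stratification factor in sections 4.3, 6.2.4 and 9.3, but is not in the 9.8 model. The documents give no evidence on the prognostic value of other candidates, so the team should justify any it adds.

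Sections 5.3.1 and 5.3.2 leave open the use of co-intervention and prohibited-intervention data in analyses. A cross-reference placing such analyses outside the main estimate would keep the sections consistent.

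The cost is one clause removed, a few sentences in 9.8 and that cross-reference, with no new data. The small downside is that the team gives up adjusting the main estimate for a striking chance imbalance, though it can still show the effect as a sensitivity analysis.

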### 6.2 Evaluations

#### 6.2.1 Screening Evaluations

Screening evaluations will be conducted by study coordinators based at outpatient facilities at [name] on the Mt. Zion campus of UCSF, which contain all equipment needed for screening assessments. Screening procedures will include a brief preliminary Screening Telephone Interview, followed by an in-person Screening Clinic Visit, completion of a 3-day voiding diary at home, and review of the diary at an in-person Baseline Clinic Visit. All screening procedures must be completed within a 90-day period in order for participants to be eligible for randomization. If screening procedures cannot be completed within 90 days, initial screening procedures must be repeated to ensure that participant eligibility has not changed prior to randomization.

### **6.2.2 Consenting Procedure**

Prior to administration of any data collection instruments, signed consent will be obtained by a research coordinator at the beginning of the Screening Clinic Visit. A single informed consent process will be used that will cover both the screening and post-randomization procedures. All participants must be able to read and understand the consent form in English and must provide written informed consent before enrolling in the study. Following the UCSF IRB-approved template (see Appendix A), the consent form will describe the purpose of the study, the procedures involved in recruiting, randomized, and monitoring participants, and the potential risks and benefits associated with participation. A study coordinator will first explain the study procedures to the potential participant, referring as necessary to the detailed IRB-approved consent form. The coordinator will then give a paper copy of the consent form to the potential participant to read. After the potential participant has read the consent form, she will be asked if she has any questions or concerns about the study. Once these questions/concerns have been addressed, the participant will be asked to sign the consent form, and will be given a copy of the consent form to take home for future reference. Coordinators will also have each participant read and sign a HIPAA authorization form granting study staff permission to access protected health information if needed. Pursuant to California Health & Safety Code 24172, each participant will also receive a copy of the Experimental Subject's Bill of Rights. A copy of the signed consent form and HIPAA authorization form will be stored in the participants' chart in locked research offices.

